UK specific data on SSP is entirely absent, with even basic data on typical length of stay, underlying aetiology and surgical referral rates having to be extrapolated from international studies out of necessity. Currently, a single centre study from Japan and a French epidemiological study provide the best estimates for length of stay in SSP(2, 3). National databases, such as the Hospital Episode Statistics (HES) database, do not distinguish between PSP and SSP, and do not provide detailed individual patient level data.

British Thoracic Society (BTS) guidelines provide clear advice on different treatment strategies for primary (PSP) and secondary (SSP) spontaneous pneumothorax, but compliance with these guidelines amongst non-respiratory healthcare professionals is reportedly low(8). Additionally, the advice on SSP is based on limited data and there are many outstanding research questions that need answering. There is no current guidance on patient selection for surgical management for persistent air leak (PAL) and recurrence prevention. Patients with SSP are typically felt to be poor surgical candidates, due to poor physiological reserves and comorbidities, but there is a lack of information about which patients would most benefit and which are most are risk. This project would identify the patient characteristics of those accepted for surgery, and their outcomes. Additionally, the management of persistent air leak is extremely problematic in this patient cohort, with no clear evidence on how best to manage. This project would capture current national practice on PAL and the impact this had on air leak duration.

Recurrence rates are felt to be higher in SSP compared to PSP, with historic and poorly evidenced cited rates between 40-50%(5), however there is no robust data to inform on this, or the factors which influence it. This project would give vital insights and help inform practice.

10

AIMS & OBJECTIVES:

To determine the characteristics, healthcare burden, management, and outcomes of secondary spontaneous pneumothorax (SSP) in UK over a 1-year period

AIMS AND OBJECTIVES:

- To determine characteristics of SSP patients admitted in study period (age, gender, underlying respiratory condition)
- To determine management of SSP in study period (procedures, recurrence prevention, surgery)
- To determine outcomes of SSP admission (length of stay, duration of air leak, mortality)

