A conservative estimate of patients with SSP presenting and identified by research staff at each site is 12 per annum (based on Hi-Spec RCT screening log(6)). Provisional anonymised HES data suggest that this may be a

considerable underestimate, demonstrating a mean of 40.5 SSP presentations/annum at the top 15 NHS Trusts. As SSP typically have substantial inpatient length of stay and are managed by Respiratory team, high identification rates are anticipated. Additionally, the opt-out consent model should maximize data capture. With 20 participating sites, we would expect a minimal of 120 patients over a 6-month period.

The recruitment target is a minimum of 120 patients per year. The LISP will run over a one-year period (recruiting for 6 months with a 6 month follow up period). Given the observational nature of this study, patients will be eligible to co-enrol in other studies if invited.

FOLLOW-UP SCHEDULE

All participants will only undergo assessment at a single time point, at enrolment ("baseline assessment"). This will be performed by a member of the study team and should be done within the first week from enrolment.

Subsequently, study data will be acquired from the medical records at two further time points, at 1-month and 6-months post enrolment. This will be conducted by the local medical research investigator. As this is a trainee-lead project, it is anticipated this will a respiratory trainee.

LONGITUDINAL INVESTIGATION OF SECONDARY PNEUMOTHORAX (LISP) PATIENT JOURNEY FLOWCHART **INSPIRE NETWORK**

Emergency attendance to hospital with secondary spontaneous pneumothorax, confirmed by radiology, with

- · spontaneous pneumothorax in presence of known or suspected lung disease
- spontaneous pneumothorax in patient ≥50 years of age and smoking history.
- iatrogenic pneumothorax
- traumatic pneumothorax

FIGURE 2: PATIENT JOURNEY FLOWCHART

DATA COLLECTION

Baseline assessment

The baseline assessment for all patients will incorporate routinely collected clinical information, such as:

- History and examination by a Respiratory physician, including duration of symptoms, co-morbidities and • past medical history, current/recent medications, smoking status including cannabis, clinical frailty score (CFS) and performance status (PS).
- CXR data- size of pneumothorax

1-month post-enrolment (+/- 14 days)

A review of participant's clinical records to collect data on key clinical outcomes, including but not exclusively, the:

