- Initial length of stay
- Digital air leak (DAL) measurement (if available)
- Analogue air leak assessment
- Number of type of interventions, including therapeutic aspirations, intercostal chest drains (ICD) insertions, blood batch, ambulatory care and surgical procedures.
- Treatment complication
- Mortality

6 month post-enrolment (+/- 14 days)

A review of participant's clinical records to collect data to identify:

- Initial Length of stay (if exceeded 1 month)
- Ipsilateral recurrence of pneumothorax

STUDY FLOW CHART:

Schedule of assessments:

Description	Investigation	Baseline	4 -week	26-week
		assessment	follow up	follow up
			assessment	assessment
			(+/- 7 days)	(+/- 4
				weeks)

Clinical review	Patient demographics	Х		
	Pneumothorax history	Х		
	Patient co-morbidities	Х		
	Assessment of PS/CFS	Х		
	Medication history	Х		
	Number of interventions		Х	
	Mortality		Х	
	Length of stay		Х	Х
Recurrence			Х	Х
Imaging	CXR	Х		
	СТ		X*	
Air leak	Analogue air leak assessment (if		Х	
assessment	available)			
	Digital air leak assessment (if		Х*	
	available)			
*-if clinically available				

DEFINITION OF END OF TRIAL

All participants will be actively followed up for 6 months after recruitment. The opt-out log will be reviewed 4 weeks after data-collection has finished. The end of the trial as a whole will be after all trial participants have completed follow up, all data queries have been resolved, the database locked and the analysis completed.

DATA HANDLING AND RECORD KEEPING

Data collection tools and source document identification

Source data will all be electronic from NHS Trust computer systems i.e., patients' medical records, laboratory and radiology reports and directly entered onto an eCRF in REDCap.

Data handling and record keeping

Data entry at will use a bespoke study database housed on the University of Bristol server, built using the validated open-source REDCap system and regularly backed up. The study investigator will facilitate data entry into the database via an electronic case report form (eCRF) with the support of the clinical team. Each participant will be allocated an unambiguous subject identification code (trial participant ID).

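### The text's condition for completing length of stay at 6 months conflicts with the schedule and, read literally, leaves open some stays of about 16 to 30 days

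*Protocol*

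**What the plan says.** The Follow-up schedule section says that data are taken from the medical records "at 1-month and 6-months post enrolment".

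The Data collection section then gives two lists:

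- Under "1-month post-enrolment (+/- 14 days", the first item is "Initial length of stay". It gives no instruction for a patient who is still in hospital.
- Under "6 month post-enrolment (+/- 14 days", the item is "Initial Length of stay (if exceeded 1 month".

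The schedule of assessments times the first review at 4 weeks with a tolerance of 7 days, and the second at 26 weeks with a tolerance of 4 weeks. It marks length of stay at both, with no condition on the second.

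Length of stay is a named outcome under Aims and objectives ("To determine outcomes of SSP admission (length of stay, duration of air leak, mortality"). It is also the fourth research question under Clinical outcomes, and one of the outcomes whose predictors are to be modelled under Analyses.

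**The concern.** The two text rules do not meet. The first review can take place before 1 month, but completion at the second review is triggered only by a stay longer than 1 month. Take a patient reviewed as an inpatient on day 16 and discharged on day 26. There is no discharge date to record at the first review, and the stay did not exceed 1 month, so the 6-month condition is not met.

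The loss would not be random. Shorter stays are complete at the first review, and stays over a month are picked up at the second. Only a band in the upper part of the distribution is exposed, and only where the site reviewed early. That could pull down the mean and upper percentiles, and could make early-reviewing sites appear to have shorter stays.

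The schedule does not contain this restriction, and nothing in the protocol says which of the two governs. Two sites could both follow the protocol and collect a named outcome differently.

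**Working it through.** The plan gives no figure of its own on this point. The only plan figure used below is the sample size, which reproduces: 20 sites × 12 patients a year × 0.5 year = 120.

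**Step 1: the exposed band.** Earliest first review = nominal day − tolerance. Exposed stays are those still open on that day that end by 1 month.

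| Window | Earliest review | Exposed stays |
|---|---|---|
| Text, 30-day month | 30 − 14 = day 16 | 16 to 30 days |
| Text, 28-day month | 28 − 14 = day 14 | 14 to 28 days |
| Text, 31-day month | 31 − 14 = day 17 | 17 to 31 days |
| Schedule, 4 weeks | 28 − 7 = day 21 | 21 to 28–31 days |

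The month length is an assumption. Choosing the schedule's window narrows the band but does not empty it.

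Reviews run from enrolment, whereas a stay runs from admission. If enrolment lags admission and the month is counted from admission, the text band narrows: 16 + 3 = 19 to 30 days for a 3-day lag, and 16 + 7 = 23 to 30 days for a 7-day lag (both lags assumed).

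**Step 2: text against schedule.** With the text condition, the band is as above. With the schedule's unconditional entry at 26 weeks, it is empty.

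**Step 3: how many patients.** The protocol gives no distribution of stays, so I assume log-normal stays with median 8 to 12 days and log-SD 0.8 to 1.0. With distribution function F, the exposed share for a review on day r is F(30) − F(r), or zero if r is 30 or later.

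Example, median 10 and log-SD 0.8, all reviews on day 16:

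Φ(ln(30/10)/0.8) − Φ(ln(16/10)/0.8) = Φ(1.373) − Φ(0.588) = 0.915 − 0.722 = 0.194, and 0.194 × 120 ≈ 23 patients.

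Averaging the same expression over equally likely review days gives 0.040 for days 16 to 44 (about 5 of 120) and 0.027 for days 21 to 35 (about 3 of 120).

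Over the whole assumed range:

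| Timing of first reviews | Share exposed | Of 120 |
|---|---|---|
| Even over text window | 3–5% | 3–6 |
| Even over schedule window | 2–3% | 2–4 |
| All on day 16 | 14–23% | 17–28 |
| All on day 21 | 6–12% | 8–14 |

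**Step 4: effect on the summaries.** Simulated at median 10 and log-SD 0.8, where the full-data mean is about 13.8 days and the 90th percentile about 28 days:

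- Even spread, exposed stays frozen at the review date: the mean is about 13.6 (text window) or 13.7 (schedule window), the median is unchanged, and the 90th percentile falls by about 1 day.
- Even spread, exposed stays dropped: the mean is about 13.3 to 13.4.
- All reviews on day 16, exposed stays frozen: the mean is 12.7 and the 90th percentile 16.
- All reviews on day 16, exposed stays dropped: the 75th percentile falls from 17.1 to 12.4.

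**Step 5: after the change.** If the 6-month item applies to every patient not discharged at the first review, every stay open on any permitted review day meets the condition. The band is empty under either window.

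**The case against.** A reader might infer that these stays are never completed under the plan. The documents do not support that, because the schedule calls for length of stay at 26 weeks for everyone. The loss arises only where a site follows the text literally, and only for patients reviewed before 1 month.

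A reader might also infer serious bias from the day-16 figures. Those need every first review to fall on the first permitted day, an assumed distribution, and a rule for freezing or dropping open stays that the protocol nowhere states. They show the extreme, not the expected effect.

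The bullet is also a short label, and its natural sense may be a stay that ran past the 1-month review. The discharge date remains in the records, the database has validation checks and a query system, and the trial ends only once "all data queries have been resolved, the database locked and the analysis completed". An investigator who found the field blank at 6 months would probably fill it in.

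Much of this stands, and it keeps the point modest. It does not remove it. The intended sense is not what the words say, and the reviews are expected to be done by local trainees across 20 sites. The query provision is general: under the literal condition, a blank 6-month entry for a 26-day stay is valid, and a value frozen at the first review looks complete, so neither need raise a query.

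**Conclusion.** The point holds as a conflict between the text and the schedule, with a loosely worded completion condition in the text. The band of about 16 to 30 days (about 21 to 30 under the schedule's window) is calendar arithmetic and depends only on the length taken for a month and on any enrolment lag.

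The patient counts and shifts in the summaries rest on the assumed log-normal stays and on the timing of reviews. With evenly spread reviews, the likely consequence is a handful of patients and a small shift in the mean and upper tail. Larger effects appear only if reviews cluster at the start of the window. It is worth correcting because length of stay is a named outcome and the correction is nearly free, not because the study's results are in serious doubt.

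**What to change.** In the 6-month list under Data collection, replace the parenthetical condition with: *if the patient had not been discharged at the first review*. The text then secures what the schedule already asks for, a completed stay for every patient, whichever review window is kept.

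The cost is one phrase. The same records are opened at 6 months to look for recurrence, so no new review or data source is needed. The eCRF is not shown; if its 6-month field is conditioned on the present wording, that condition should be changed to match.

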Inclusion criteria	Emergency attendance to hospital with secondary spontaneous		
	pneumothorax, confirmed by radiology, with SSP defined as:		
	 spontaneous pneumothorax in presence of known or 		
	suspected lung disease OR		
	 spontaneous pneumothorax in patient ≥50 years of age and 		
	smoking history		
Exclusion criteria	Exclusion		
	 age <16 years of age 		
	iatrogenic pneumothorax		
	traumatic pneumothorax		

FUNDING AND SUPPORT:

Funders	Financial and non-financial support given
Rocket Medical plc	Unrestricted research grant and equipment
[name]	
Watford	
[name]	
[contact]	

Role of trial Sponsor and Funder:

The Sponsor and Funders have no role or remit in the trial design, conduct, data analysis and interpretation, manuscript writing or dissemination of results.

Protocol contributors:

Protocol authors: [name], [name], [name], [name], [name].

External Peer review

National INSPIRE committee: [name], [name], [name], [name], [name]

STUDY FLOW CHART

PLAIN ENGLISH SUMMARY

Background

Secondary spontaneous pneumothorax (SSP) is a medical emergency where an abnormal collection of air develops in the space between the lung and the chest wall, causing lung collapse. This occurs in patients with existing lung disease such as Chronic obstructive pulmonary disease (COPD). In the UK, patients with SSP are usually treated by inserting a drain into the chest to remove the air. The drain is stitched in place and left until the air is completely removed. The drain typically remains in place for over a week, leading to long hospital stays. Sometimes these patients need surgery to help stop the air leaking into the lung, but it is also recognised that these patients may not be fit for major surgery.

Unfortunately, we don't have data from UK patients about key consequences of developing a secondary spontaneous pneumothorax. For example, we don't know how long patients stay in hospital, how many go for surgery, and how many develop complications. With this information we can better plan for care, but also look at why some patients stay longer in hospital and why some patients need surgery, whilst others don't.

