- To determine factors, including inter-site variability, influencing surgical referral and acceptance rates for air leak and recurrence management
- To determine factors influencing short-term recurrence rates

Research questions which may be addressed as part of the study are listed below.

CLINICAL OUTCOMES

- 1. What are the demographics of the SSP population in the UK (age, gender, underlying aetiology, previous SSP, lung function)?
- 2. What are the size and location of pneumothorax on chest x-ray (side, maximum intrapleural distance, hilar intrapleural distance)?
- 3. How are the patients managed during their inpatient stay (initial management, prolonged air leak management, recurrence prevention interventions, surgical referral, surgical intervention)?
- 4. What are the patients' length of stay?
- 5. What are the patients' duration of air leak?
- 6. What are the patients' mortality rate?
- 7. What proportion are referred and receive surgery?
- 8. What are the patients 6-month ipsilateral recurrence rates?
- 9. What is the expertise available at hospital (presence of onsite thoracic surgical unit, dedicated pleural clinic)?

METHODOLOGY

STUDY DESIGN

LISP is a multi-centre, prospective, longitudinal cohort study of patients diagnosed with SSP.

STUDY POPULATION

Population of interest: patients presenting to hospital with secondary spontaneous pneumothorax.

Inclusion

Emergency attendance to hospital with secondary spontaneous pneumothorax, confirmed by radiology, with SSP defined as:

- spontaneous pneumothorax in presence of known or suspected lung disease OR
- spontaneous pneumothorax in patient \geq 50 years of age and smoking history.

Exclusion

- age <16 years of age
- iatrogenic pneumothorax
- traumatic pneumothorax

RECRUITMENT

Recruitment procedure

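### Six-month recurrence is read at a fixed date after enrolment and analysed by logistic regression, although the index pneumothorax is still open at enrolment, so time at risk is unequal and re-collapse is not separated from recurrence

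*Protocol*

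**What the plan says.** Five parts of the protocol bear on this point.

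- **Outcome.** Clinical Outcomes, item 8, asks "What are the patients 6-month ipsilateral recurrence rates". Aims and Objectives includes "To determine factors influencing short-term recurrence rates". Neither gives a time origin or defines recurrence.
- **Timing.** Under Follow-up Schedule, data are taken from the records "at two further time points, at 1-month and 6-months post enrolment". Under Data Collection, the second review is headed "6 month post-enrolment (+/- 14 days") and lists "Ipsilateral recurrence of pneumothorax". The schedule of assessments gives the 26-week review a window of +/- 4 weeks and also asks for recurrence at the 4-week review.
- **State at enrolment.** The inclusion criterion is an emergency attendance with a radiologically confirmed pneumothorax, so the index episode is open.
- **Length of the index episode.** The Plain English Summary says "The drain typically remains in place for over a week, leading to long hospital stays". The 6-month review provides for "Initial Length of stay (if exceeded 1 month").
- **Analysis.** Under Analyses, predictors of recurrence, among other outcomes, are to be found by multivariate logistic regression. The parameters named are underlying lung disease, FEV1 and recurrent pneumothorax, and the list is left open.

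**The concern.** A recurrence on the same side needs prior resolution. If recurrence is read at a fixed date after enrolment, a patient's time at risk is the follow-up length minus the days that the index episode stayed open. A patient who resolves on day 3 has 179 days at risk, and one who resolves on day 45 has 137. A yes/no outcome in a logistic model treats them alike. Any factor that delays resolution then has its association with recurrence pulled downwards by the design.

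A second problem works the other way. At the 4-week review some index episodes may still be open, and nothing tells the data collector whether a re-collapse or a re-drainage counts as recurrence. If it is counted, patients with long leaks gain events that are failures of the first treatment.

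At stake are the 6-month recurrence rate and the objective on factors behind short-term recurrence, a topic on which the Background says robust data are lacking.

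**Working it through.** **The plan's own figure.** The protocol states no power and no expected recurrence figure. Its study size reproduces: 20 sites x 12 patients per year x 0.5 year = 120.

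**Inputs from the protocol.** Follow-up is 6 months from recruitment, taken as 182 days. Drains typically stay in for more than 7 days. Index stays above 1 month are provided for. The Background cites recurrence of 40-50% without a time horizon.

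**Assumptions.** The true risk over a full 182 days after resolution, R, is 20%, 30% or 45% and is the same in every patient. The hazard is either constant (k = 1) or front-loaded (Weibull shape k = 0.5). Resolution days d are illustrative.

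**Step 1: time at risk alone.** F(t) = 1 - exp(-L x (t/182)^k), with L = -ln(1 - R). The spurious risk ratio for resolution on day d against day 3 is F(182 - d)/F(179).

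Example with R = 45%, k = 1 and d = 45: L = 0.598, F(179) = 0.445, F(137) = 0.362, ratio 0.815.

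| Resolution day | Days at risk | Risk ratio, constant hazard | Risk ratio, front-loaded |
|---|---|---|---|
| 8 | 174 | 0.975-0.979 | 0.987-0.990 |
| 14 | 168 | 0.945-0.954 | 0.972-0.977 |
| 28 | 154 | 0.87-0.89 | 0.93-0.95 |
| 45 | 137 | 0.78-0.82 | 0.89-0.90 |

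Ranges run over R from 20% to 45%. If time is counted from resolution and modelled as time at risk, each ratio is 1.00.

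**Step 2: would it produce a false predictor?** Take a constant hazard, R of 20-45%, and 120 patients. If 60 patients are open for 5 days and 60 for 30 days, a two-sided 5% test rejects in about 5-8% of studies. If 90 are open for 5 days and 30 for 60 days, it rejects in about 9-18%.

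**Step 3: the opposing bias.** Let p1 be the risk with 5 days open and p2 the risk with a long leak. The share m of long-leak patients whose unresolved episode must be miscounted as recurrence to cancel the deficit is m = (p1 - p2)/(1 - p2). With R = 45% and 30 days open, (0.441 - 0.393)/(1 - 0.393) = 0.079. Over R = 20% and 45%, m is 3.0-7.9% for a 30-day leak and 6.5-16.5% for a 60-day leak. A larger share reverses the sign.

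**Step 4: the review window.** With R = 45% and a constant hazard, a review 14 days early or late moves the expected risk to 42.4% or 47.5%. A review 28 days early or late moves it to 39.7% or 49.8%. With R = 20% the pairs are 18.6% and 21.4%, and 17.2% and 22.7%. The choice between the two stated windows is therefore not trivial.

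**The case against.** The strongest reply has four parts.

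- **Definition.** The text fixes when records are read, not the time origin of the rate. A definition of recurrence is commonly left to a statistical analysis plan, and recurrence within 6 months of presentation is a legitimate descriptive quantity. This stands as far as it goes. But the protocol itself names logistic regression and asks for recurrence at 4 weeks, and a later analysis plan cannot restore dates that were never collected.
- **Data already recorded.** Air-leak duration is an outcome and the 1-month list is not exhaustive, so the end of the leak may be recorded for many patients. A reader might infer that no such date will exist; the protocol does not support that. The gap is in leaks that outlast the 1-month review, because air leak is marked only there and the 6-month review lists only length of stay and recurrence. Length of stay is a weak substitute, since ambulatory care is among the listed interventions and discharge need not mean resolution.
- **Direction.** A reader might infer that patients with long leaks will look protected. Step 3 shows why this does not follow: a modest share of miscounted re-collapses cancels or reverses the effect.
- **Size.** For leaks near the protocol's own figure of over a week, the effect is about 1-3%. Providing for stays beyond a month does not show that they are common. Leak duration is also not a named predictor, so bias in a named factor depends on how far its groups differ in open time. All of this stands and limits the point.

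**Conclusion.** The point holds in a limited form. Followed as written, the plan mixes unequal times at risk and can count an unresolved index episode as a recurrence. The two errors oppose each other and the net direction cannot be stated. The time-at-risk part alone is negligible for leaks of one to two weeks. It reaches a risk ratio of 0.87-0.95 at day 28 and 0.78-0.90 at day 45, and would rarely be significant alone with 120 patients. It is a distortion of estimates more than a source of false positives.

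A reader might take a spurious protection of 5-22% to apply to the planned analysis as a whole. It does not: that range belongs to individual contrasts of day 28 or day 45 against day 3.

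The sizes rest on assumed 6-month risks, hazard shapes and leak durations, because the protocol gives none of these. The enrolment-anchored review, the open index episode and the logistic model are all in the text. The change is worth making before data collection because it is cheap then and may be impossible later.

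**What to change.** 1. Record the date on which the index episode resolved for every patient, including leaks that outlast the 1-month review. State how the date is set for patients managed without a drain.
2. Define recurrence as a new radiologically confirmed ipsilateral pneumothorax after that date. Record earlier re-collapse or re-drainage as a separate item. Report episodes that never resolve separately, not as recurrence-free.
3. Record dates of recurrence and of death up to the 6-month review. The schedule now marks mortality only at the 4-week review.
4. Replace logistic regression for recurrence with a time-to-event analysis from resolution, censored at the date of the record review, with death as a competing event. Moving the clock while keeping the logistic model would not help, because censoring has no role in it.
5. Reconcile the 6-month review window, which is +/- 14 days in the text and +/- 4 weeks in the schedule.

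The cost is a few more dates from records already being reviewed, and a definition in the protocol. The small downside is that late resolvers contribute less than 6 months of follow-up after resolution.

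### The protocol promises active 6-month follow-up but describes only Trust record review, and no listed 6-month item shows whether a patient's recurrence status is known

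*Protocol*

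**What the plan says.** Definition of end of trial states: "All participants will be actively followed up for 6 months after recruitment".

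The sections that set out the procedure describe no contact with the patient after baseline:

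- Follow-up schedule: "All participants will only undergo assessment at a single time point, at enrolment". After that, "study data will be acquired from the medical records at two further time points, at 1-month and 6-months post enrolment". On who does it: "This will be conducted by the local medical research investigator".
- Data collection, 6-month step: "A review of participant's clinical records to collect data to identify" two things, the initial length of stay if it exceeded one month, and "Ipsilateral recurrence of pneumothorax".
- Data handling and record keeping: "Source data will all be electronic from NHS Trust computer systems i.e., patients' medical records, laboratory and radiology reports".

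The schedule of assessments marks recurrence at 4 and 26 weeks and mortality at 4 weeks only. Its imaging rows are chest X-ray at baseline and CT, if available, at 4 weeks.

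The 6-month ipsilateral recurrence rate is item 8 of the Clinical outcomes. Factors influencing short-term recurrence are an objective, and Analyses names recurrence among the outcomes for logistic regression.

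**The concern.** *Actively* tells a reader that someone establishes each patient's state at 6 months. The procedure does not do that. It looks for a recurrence in the records and, as listed, notes nothing else that bears on recurrence status. The protocol mentions no visit, call, general practice record, search of other Trusts or national linkage.

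This matters because recurrence is one of the reasons for the study. The Background section says that existing recurrence rates are poorly evidenced and that this project would help to fill the gap. If known recurrence-free patients cannot be told apart from patients about whom nothing is known, the new rate has an uncertainty that its confidence interval does not show. An analysis plan can set a coding rule, but it cannot separate two states that the data collection has merged.

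**Working it through.** **1. The passages side by side**

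| Question | Definition of end of trial | Follow-up schedule, Data collection, Data handling |
|---|---|---|
| How is the patient followed? | Actively, for 6 months | One assessment at enrolment, then record review at 1 and 6 months |
| Who supplies the 6-month information? | Not stated | Local investigator, from NHS Trust electronic systems |
| Is 6-month status known? | Implied for all | No item listed (no last contact, last imaging or status-known field) |
| Death after the 4-week review? | Not stated | Not a scheduled item |

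The two descriptions of follow-up cannot both be right.

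**2. Inputs for an illustration of size**

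- Number of patients, from Recruitment target: 20 sites × 12 per year × 0.5 year = 120. This reproduces the protocol's figure.
- True recurrence rate p: 40% and 50%, the ends of the range cited in Background. The protocol calls that range historic and poorly evidenced and gives it no time horizon, so it serves only as an illustration.
- Share m of recurrences absent from the reviewed records: not in the protocol. Assumed range 5% to 30%.
- Share v of recurrence-free patients with no later record: not in the protocol. Assumed values 10% and 30%.

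**3. Sampling error**

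95% half-width = 1.96 × √(p(1 − p)/120).

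- p = 40%: 1.96 × √(0.4 × 0.6/120) = 8.8 points.
- p = 50%: 1.96 × √(0.5 × 0.5/120) = 8.9 points.

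**4. If patients without a record are counted as 'no'**

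Observed rate = p × (1 − m).

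| Share missed, m | True 40% observed as | True 50% observed as |
|---|---|---|
| 5% | 38% | 47.5% |
| 10% | 36% | 45% |
| 20% | 32% | 40% |
| 30% | 28% | 35% |

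The bias is p × m, so it equals the half-width at m = 8.8/40 = 22% for a true 40%, and at m = 8.9/50 = 18% for a true 50%. In short, it matches the sampling error when about one recurrence in five is missed.

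**5. If patients without a record are excluded**

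Observed rate = p(1 − m) / [p(1 − m) + (1 − p)(1 − v)].

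With p = 40%:

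- m = 10%, v = 10%: 0.36 / (0.36 + 0.54) = 40.0%. No bias, because records are equally complete in both groups.
- m = 10%, v = 30%: 0.36 / (0.36 + 0.42) = 46.2%. Too high.

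The second case is the more natural one, since a treated recurrence creates a record and an uneventful course may not. The direction of the bias therefore depends on how these patients are handled.

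**The case against.** The strongest reply is that the record-based method is stated openly in several places and that one adverb in an end-of-trial definition does not govern ascertainment. On this view the point is a small correction of wording, and the coding of unknown outcomes belongs in an analysis plan that is not at hand.

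Much of this stands, and it rules out some stronger readings:

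- A reader might infer that patients without a later record will count as recurrence-free, so that the rate is a lower bound. The protocol gives no such rule. Logistic regression does not force one, because patients with unknown outcome can be left out, and step 5 shows that this can push the rate up.
- A reader might infer that the rate is being presented as complete. Nothing supports this beyond the word *actively*.
- A reader might expect features linked to re-attendance, such as living nearby or clinic follow-up, to emerge as false risk factors. The parameters named in Analyses are underlying lung disease, FEV1 and recurrent pneumothorax. The list is not closed, but neither of those features is named as a collected item, so this is speculation.

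The illustration is also open to challenge. Secondary pneumothorax is described as an emergency in unwell patients, which argues against many recurrences never reaching hospital. At a lower assumed true rate of 30%, missing 10% or 20% costs 3 or 6 points, below the half-width of 8.2. Only 30% missed (9 points) exceeds it.

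It may also be said that if the reviewer can tell the two states apart in the records, they do not look the same. That is correct about the records. It is the listed data items that merge them, and for that reason the matter is more than wording and cannot be left wholly to an analysis plan.

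**Conclusion.** The point holds in limited form. The contradiction between active follow-up and record review is certain from the text. It is also clear that no listed 6-month item distinguishes known absence of recurrence from absence of information, or records a death after the 4-week review. The source is described only as NHS Trust systems reviewed locally, without saying whether other Trusts' records are searched, so a recurrence treated elsewhere can be missed.

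Neither the direction nor the size of any bias is established. If 20% of recurrences were missed and counted as 'no', a true 40% would be observed as 32%, an 8-point error beside a half-width of 8.8. If patients without a record were excluded, with 10% of recurrent and 30% of recurrence-free patients lacking a record, the same 40% would be observed as 46.2%. All the missing shares are assumptions, and the 40% is the protocol's own loosely supported figure. The point does not undermine the rest of the study, but it should be corrected because recurrence is a listed outcome and a modelled endpoint.

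**What to change.** 1. In Definition of end of trial, say that participants are followed by review of hospital records for 6 months, in line with the Follow-up schedule.
2. Define the outcome as *recorded* ipsilateral recurrence, and state which records are searched (recruiting Trust only, or others as well).
3. Add one field to the 6-month review with four states:
   - recurrence recorded;
   - no recurrence, with a documented contact or chest imaging at or near 6 months;
   - died without recorded recurrence, with date;
   - no record since discharge.

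   Tie 'at or near 6 months' to a single window. Data collection gives ±14 days and the schedule of assessments ±4 weeks, and these need reconciling.
4. Report the number of patients in each state. Give the recurrence rate with patients in the last state counted as 'no' and, as a sensitivity estimate, among patients with known status. Say that the second figure is likely to run high and is not a corrected rate. State how deaths enter each denominator.

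The cost is a protocol wording change, one extra field from a review already planned, and a range in place of a single figure. It needs no patient contact and no change to care or to the opt-out consent.
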